### **Screening and Assessment for Nutritional Status**

Screening: we will use the Malnutrition Universal Screening Tool (MUST score) [9] to identify patients at nutritional risk. If the patient scores <1 on the MUST score, they will be assigned to **universal support**.

Assessment: Patients scoring >1 on MUST will be referred to a student dietitian for a nutrition assessment. This may result in the prescription of oral nutritional supplements. This will include using the patient-generated and professional component of the Patient-Generated Subjective Global Assessment (PG-SGA) [10]. They will additionally perform a hand grip strength test to enable a nutritional diagnosis and direct care in accordance with the Nutrition Care Process mode [11] and will be allocated to **targeted or specialist groups** accordingly.

### **Screening and Assessment for Psychological Status:**

Screening: Patients will be screened using the General Anxiety Disorder Assessment (GAD-7) [12], the Patient Health Questionnaire 9 (PHQ-9) [13] and the 'need for help' emotions thermometer [14]. Patients scoring <9 on the GAD-7 or PHQ-9 and/ or <5 on the 'need for help' item of the emotions thermometer will be assigned to **universal support**.

Assessment: Patients scoring >9 on the GAD-7 or PHQ-9, and/or >5 on the 'need for help' item of the emotions thermometer will be invited to speak to a student clinical psychologist to determine **targeted or specialist** allocation.

Based on initial screening, individuals will be categorised into a universal, targeted or specialist group and will receive an intervention based on the criteria identified in Table 2. **Table 2. Personalised Care Plans Delivered based on Needs Assessment**

	Universal	Targeted	Specialist

Exercise	
Home-based exercise (supported by regular phone/video calls with student physios/sports rehabilitation therapists);
 
Increasing frequency, intensity, and duration incrementally to achieve a minimum of 150 min per week of moderate/vigorous physical activity (MVPA)
 
In addition, 2 sessions of resistance training per week.
 
Sedentary time:replacing daily sittingtime with standing/moving time.
	
Delivered by student physios/sports rehabilitates group-based training (F2F - attend Hip-Hub sports injuries clinic at UoH or delivered virtually through Teams).
 
3 sessions per week (total home and facility-based sessions) of aerobic exercise training (minimum 20 minutes per session) (moderate or HIIT).
 
In addition, 2 sessions of resistance training per week.
 
Sedentary time:replacing daily sittingtime with standing/moving time (use activity diaries)
	
Delivered 1:1 in F2F Hip-Hub setting.
 
3 sessions per week (including x1 home session) aerobic training (minimum of 20 min per session at moderate intensity).
 
Additionally, if able, 2 resistance training sessions per week.

-----------------	---	---	--

Nutrition	
Dietary advice including basic principles. Supported by regular phone calls / video calls with student nutritionists.
	
Dietetic/nutrition counselling/advice with a student dietitian, including dietary modification, management of nutrition impact factors and oral nutritional supplements. This will be in addition to food fortification advice as per best clinical practice.
	
Artificial nutrition support recommended by a dietitian as per best clinical practice. EXCLUDED FROM INTERVENTION.

------------------	--	--	--

Psychological Support	Signposting to psychological support resources (such as relaxation and mindfulness apps) or as printed resources as appropriate. Supported by regular student-led phone/ video calls	Facilitated peer-group support emphasising mutual problem solving, plus a package of up to 6 1:1 sessions with a student clinical psychologist focusing on self-regulation of stress/anxiety, self compassion and self-soothing skills personalised to individual needs. This is consistent with typical level 2 psychological support practice as per NICE Guidance[64].	Full clinical psychological assessment and individualised intervention plan with a clinical psychologist (or equivalent), as per best clinical practice and Level 3/4 of NICE guidance [64]. EXCLUDED FROM INTERVENTION
------------------------------	--	---	---

If an individual is identified as being in the Specialist group for Nutrition or Psychological Support they would be re-referred via HUTH for specialist care through usu-

al professional service channels. Nutrition/dietetics/clinical psychology students would not be involved in their future care/treatment.

- **Theoretical/Conceptual Framework:**

To maximise patient engagement and adherence a person-centred approach to behaviour change support will be employed across all components (exercise, nutrition and psychological support) [15]. Students will be encouraged to use a motivational-type interviewing, and adopt the COM-B model of behaviour change [16]. We will focus on enhancing participants' self-efficacy (confidence) to engage in new behaviours as well as developing strategies and action plans that meet their priorities and personal circumstances. Approaches will be individualised depending on the level of patient autonomy required to adhere to the PCPs.

- **Anticipated impact:**

BoneFit will benefit the NHS and patients in 4 ways: 1) informing clinical guidelines and developing the evidence-base around multimodal prehabilitation for patients requiring orthopaedic surgery; 2) improving local patient care and service delivery through enhancing equity of access to services and building on the principles required to deliver effective, safe services. Supporting patients who would benefit from optimisation of co-morbidities and needs-based multimodal PCPs, thereby helping them "wait well" for surgery; 3) identifying and delivering education, training and advocacy for student healthcare professionals; 4) local workforce transformation through informing the development of new service pathways. Further funding from national (NIHR, MRC, orthopaedic charities) and local/regional sources will be sought if we can identify that the pathway is successful in terms of improving patient outcomes.

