All students will be working under the support and guidance of trained clinical professionals in physiotherapy, sports therapy, nutrition/dietetics, and clinical psychology or clinical exercise physiology. Student-patient interactions will be delivered either in a face-to-face individual or group setting, virtual (one-to-one or group-based using Teams or equivalent) or via telephone. Sessions will mainly be delivered live although some pre-recorded material will be used to supplement live sessions and an online resources library will be built up over time.

Outcome measures for each of the three core components (exercise, nutrition and clinical psychology) will be evaluated at 5 timepoints (initial surgical referral e.g. 18 months from surgery; baseline [2 months from surgery], immediately prior to surgery [2 to 10 days], and 3 and 12 months after surgery). See Table 1 to identify which outcome measures will be recorded. At initial surgical referral, DASI will be completed remotely. However, the remaining 4 timepoints will require face-to-face interactions and more in-depth investigations.

**Table 1.** Outcome and timepoints assessments for individuals recruited to BoneFit

Variable/ Timepoint	2 months from surgery	2-10 days prior to surgery	3 months post op	12 months post op
Physical/ Exercise				
DASI	✓		✓	✓
ISWT	✓	✓	✓	✓
Timed up and go	✓	✓	✓	✓
Hand-grip strength	✓	✓	✓	✓
HOOS-12 or KOOS-12	✓	✓	✓	✓
Nutrition				
MUST	✓	✓	✓	✓
PG-SGA	✓	✓	✓	✓
Clinical Psychology				
EQ-5D-5L (QoL)	✓	✓	✓	✓

GAD-7	✓	✓	✓	✓
PHQ-9	✓	✓	✓	✓
Emotions thermometer	✓	✓	✓	✓
Clinical outcomes				
Length of hospital stay			✓	✓
Complications			✓	✓
Re-admission rates			✓	✓
VAS pain scale	✓	✓	✓	✓

DASI - Duke Activity Score Index; ISWT: incremental shuttle walk test; VAS: visual analogue scale; MUST: malnutrition universal screening tool; PG-SGA: patient-generated global assessment; GAD-7: generalised anxiety disorder assessment; PHQ-9: depression test score; EQ-5D-5L: health and quality of life questionnaire; HOOS-12: hip disability and osteoarthritis outcome score-12; KOOS-12: knee injury and osteoarthritis outcome score-12.

At initial surgical referral, all participants referred for BoneFit will receive existing ERAS guidance on developing healthier lifestyle choices in preparation for surgery

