### **Sample Size and Process Evaluation:**

Feasibility studies are typically unpowered, based on similar studies, we will aim to recruit 25 participants to the BoneFit intervention and 25 usual-care controls (n=50).

A concurrent mixed methods process evaluation will explore safety, implementation, delivery, and acceptability of the intervention. We will use semi-structured interviews with participants and practitioners along with process data to assess:

- Barriers to recruitment;
- Acceptability and adherence to the intervention (dose received);
- Intervention delivery (fidelity);
- How the intervention was embedded into clinical practice;
- Safety outcomes: will include adverse events and serious adverse events;
- We will collect quantitative process data on safety, screening and recruitment, fidelity and dose/drop-out which will enable discussions with clinical teams to identify remedial actions to improve recruitment, retention, and fidelity.

We will conduct a pilot feasibility study of the BoneFit intervention which will take approximately 3 years to complete (including all 12-month follow up visits).

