### **Screening and Assessment for Exercise/Fitness/Functional Capacity:**

Screening: We will use the Duke Activity Status Index (DASI) [7] to screen for reduced functional capacity. Patients with a DASI score > 34 are at low risk and will be assigned to **universal support**, those with a DASI score <34 will be referred for an assessment.

Assessment: An incremental shuttle walk test (ISWT)[8] will be performed to assess patients' functional capacity. Patients with ISWT distance of <475m will be assigned to **targeted** intervention. Patients with a ISWT distance of <400m or patients with a medical comorbidity that necessitates supervised exercise will be assigned to **specialist** intervention. If a patient is deemed unsuitable to complete the ISWT by the clinical supervisor due to functional limitations or progressive pain, we will ask them to just undertake a Timed Up and Go test and use this to screen into targeted (<18 seconds), or specialist groups (>=18 seconds).

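### Patients placed in the Specialist exercise tier because a comorbidity requires supervision have one of three weekly aerobic sessions at home, with no supervision described for it

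*Protocol*

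**What the plan says.** The section Screening and Assessment for Exercise/Fitness/Functional Capacity sets the entry criteria for the Specialist tier. Two routes share one sentence: "Patients with a ISWT distance of <400m or patients with a medical comorbidity that necessitates supervised exercise will be assigned to" the Specialist intervention. A third serves patients judged unsuitable for the ISWT, who take the Timed Up and Go test instead; the protocol will "use this to screen into targeted (<18 seconds), or specialist groups (>=18 seconds".

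Table 2 describes what each tier receives. The Specialist exercise cell opens with the mode of delivery, "Delivered 1:1 in F2F Hip-Hub setting", and follows it with the aerobic schedule, "3 sessions per week (including x1 home session) aerobic training (minimum of 20 min per session at moderate intensity". Two weekly resistance sessions are added for those able to do them, with no separate statement of place. The cell does not distinguish between entry routes.

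The delivery text before Table 1 also allows student contact with patients in general to be face to face, "virtual (one-to-one or group-based using Teams or equivalent) or via telephone".

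**The concern.** The comorbidity route exists because those patients are judged to need supervision when they exercise. The schedule they are then given places part of the aerobic training at home, and the protocol does not say who supervises that part, or by what means. Followed as written, the schedule departs from the protocol's own criterion for this subgroup.

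Two things are at stake. The first is safety: the criterion is a safeguard, and the delivery plan does not show how it is kept in every scheduled session. The second is the primary objective. Study Outcomes includes the share of sessions delivered and the fidelity of delivery in feasibility, and the process evaluation adds dose received. Those measures need one clear description of what a Specialist patient should receive. That description defines the intervention, so it belongs in the protocol and is not a detail for a statistical analysis plan.

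**Working it through.** The protocol states no figure to reproduce, and no power or alpha calculation is involved (Sample Size and Process Evaluation: "Feasibility studies are typically unpowered"). The check compares the texts and adds a simple count.

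**Step 1. Entry routes against the need for supervision** (exercise screening section)

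| Route into Specialist | Need for supervision stated? |
|---|---|
| ISWT < 400 m | No |
| Comorbidity requiring supervised exercise | Yes |
| Timed Up and Go ≥ 18 s, ISWT unsuitable | No |

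**Step 2. Schedule** (Table 2, Exercise, Specialist)

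- Aerobic sessions per week: 3, of which 1 is at home.
- Sessions left for the Hip-Hub: 3 − 1 = 2.
- Share at home: 1/3 = 33%.
- Minimum aerobic time: 3 × 20 = 60 minutes per week, of which 1 × 20 = 20 minutes is at home.

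The resistance sessions are left out of the count because they depend on ability and their place is not stated separately.

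**Step 3. Is supervision of the home session described anywhere?**

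- The Specialist exercise cell names only 1:1 face-to-face delivery at the Hip-Hub.
- The other exercise cells name remote contact where it is meant. Universal is backed by phone or video calls. Targeted may be run virtually, and its schedule is "3 sessions per week (total home and facility-based sessions) of aerobic exercise training".
- The general permission for virtual or telephone contact is not tied to the Specialist home session.
- The regular student contact in the description of the service is there to check fidelity and compliance. It is not described as supervision of exercise.

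**Step 4. Do the eligibility rules remove the affected patients?** No. The exclusion criteria cover conditions in which moderate to vigorous exercise is contraindicated, and referral is limited to operative risk scores of 0 to 6. A comorbidity that calls for supervision is neither of these, and the screening section expressly places such patients in the tier.

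**Result.** The criterion and the schedule conflict for one of the three routes, over one third of the aerobic sessions.

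**The case against.** The strongest reply is that the Specialist cell reads naturally as a whole. The first line gives the usual mode of delivery and the second openly qualifies it: two Hip-Hub sessions and one at home. The Targeted cell is built the same way. This stands as far as the cell itself goes. It does not answer the screening section, because the comorbidity-route patient still has a scheduled session for which no supervision is described.

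The reply also disposes of a stronger inference about fidelity. A reader might conclude that fidelity has two rival references, so that perfect compliance with the schedule could score only two of three aerobic sessions as delivered to plan. That requires scoring against the first line while ignoring the second, and the protocol defines no such score. A home session carried out as scheduled can fairly be counted as compliant. What remains is that the two lines should be worded to agree.

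A second reply is that the protocol never says the home session is unsupervised. It allows remote one-to-one contact, says that sessions are mainly live, and has students working under trained professionals. This also stands: the text is silent on the point. It would therefore be wrong to say that the protocol prescribes unsupervised exercise. The general provisions leave room for supervision but do not supply it for this session.

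A third reply is that few patients may be affected. The protocol gives no number, so this can be neither confirmed nor used to dismiss the point.

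**Conclusion.** The point holds for the comorbidity route only. For those patients 1 of 3 weekly aerobic sessions, at least 20 of 60 minutes, lies outside the stated face-to-face setting, with no supervision described and no exception made. That conflicts with the reason for their assignment and should be corrected.

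A reader might infer that the whole Specialist tier is for patients who need supervised exercise, so that the schedule contradicts the purpose of the tier. The documents do not support this, because the ISWT and Timed Up and Go routes state no need for supervision.

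Nor can the one-third share be turned into a total number of home sessions per patient. The protocol gives neither a programme length nor a start day, and it places contact, invitation and screening before the care package begins.

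The conclusion assumes that the schedule in Table 2 applies to every Specialist patient, as the cell is written. The number affected is unknown; the only bound in the protocol is the planned 25 intervention participants.

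**What to change.** Reconcile the exercise screening section with the Specialist exercise cell of Table 2:

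- State whether the home session applies to patients assigned because of a comorbidity requiring supervision.
- If it does, state how the supervision criterion is met in that session.
- Word the delivery line to match the session schedule, so that sessions delivered and fidelity are scored against one description.

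The clinical supervisors decide the rule; no particular arrangement is proposed here.

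The cost is a few words in two places. If the decision changes where or how the session takes place, there may also be some effect on scheduling. Its size cannot be given, because the number of patients entering by this route is not stated.

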#### Identification of participants:

Participants awaiting TKR/THR surgery will be provided with PIS V4 regarding BoneFit during routine clinics at Castle Hill hospital. Contact details of the BoneFit team are included and interested parties are encouraged to contact the team. Interested

parties will be invited to the University of Hull for consenting, baseline assessments, and allocation to the intervention or control groups. Hull University Teaching Hospitals Trust staff are only required to bring the trial to the attention of suitable patients at routine THR and TKR clinics and direct them to the participant information sheets. Interested parties should then contact the BoneFit team.

Arrangements for the collection, use, sharing, security and integrity of participant data:

The BoneFit team at the University of Hull may require limited patient data from NHS organisations including Hull University Teaching Hospitals Trust. All data requested will be anonymised and each patient will receive a unique identification code. The University will only request data that is pertinent to the BoneFit intervention. For example, details of psychological interventions undertaken as a consequence of BoneFit screening into universal, targeted or specialist groups. Information requested for targeted interventions would include number of sessions undertaken, intervention details, and intervention outcomes following initial screening. NHS organisation could provide this information in the form of a brief summary statement and there is certainly no requirement for University staff to receive patient notes. This has been discussed with the Clinical Psychology team at HUTHT.

